tDCS is a safe, non-invasive, and painless form of neurostimulation that involves applying a weak electrical current to the brain via two electrodes (the anode and the cathode) placed on the scalp. A low-intensity current is passed through these two electrodes to target specific areas of the brain. The anode enhances the likelihood of neuronal firing, likely due to depolarization of cortical neurons, whereas the cathode decreases the likelihood, likely due to hyperpolarization of cortical neurons (Nitsche et al., 2008). The cerebral excitability induced by tDCS can be long-lasting and last for up to several hours after tDCS administration (Nitsche et al., 2008). Research suggests the after effects of tDCS are induced through the modulation of sodium- and calcium-dependent channels and N-methyl-D-aspartate (NMDA)-receptor activity (Liebetanz & Liebetanz, 2002). Enhancing the neuronal firing rate via A-tDCS promotes mechanisms that underlie long-term potentiation (a persistent strengthening of synapses following stimulation of synaptic activity) and long-term depression (a reduction of synaptic activity). Both long-term potentiation and depression are critical for learning and memory. Moreover, research in healthy participants has shown one tDCS session modulates large-scale patterns of resting-state connectivity in brain regions close to the stimulation sites and in brain regions far from the stimulation sites (Keeser et al., 2011). In addition to the evidence demonstrating tDCS can reliably improve language outcomes in individuals with post-stroke aphasia, this technology allows a realistic sham stimulation, making it possible to carry out double blind clinical trials. In the sham condition, stimulation is applied for 30 seconds, and then rapidly ramped down. The participant generally only feels the first 30 seconds of real or sham stimulation, and so cannot distinguish the two conditions. The distinct timing of stimulation for sham versus real (20 minute) stimulation can be applied via the Soterix tDCS device, so that the experimenter also is blinded to the condition.

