Visit 3-4: These sessions involve detailed language testing (see below) including computerized naming assessments. This battery will be the baseline language testing. A screening task will be administered prior to the baseline language testing. Participants must achieve at least 65% accuracy on screening task (comparable to treatment task) on 1 of 3 attempts. The screening test is administered to ensure that the participant understands the treatment task requirement. The probability that a patient will achieve $>65\%$ accuracy by chance on each of the three tries is low: $p<0.05$. If a participant is unable to reach this level of accuracy, study enrollment will be discontinued. A naming test will also be administered as part of baseline testing examining the ability to name nouns and verbs from pictures. Participants who's correct naming score exceeds an average of 80% accuracy will be excluded to leave at least a 20% improvement margin. That is, participants who already score close to ceiling may have limited room for naming improvement.

Visit 5-19: These sessions will involve the treatment sessions for the first intervention period. Prior to the start of treatment, participants will be randomly assigned to receive either "tDCS then sham" or "sham then tDCS". For example, if a participant is randomly assigned to received "tDCS then sham", the first intervention period of 15 sessions will be tDCS+ language treatment and the second intervention period will be 15 sessions of sham + language treatment.

Date: 01/11/2019
Principal Investigator: [name]
Application Number: IRB00174879

Visit 20: This visit will involve 1 week post treatment language testing. This visit will be similar to Visits 3-4.

Visit 21: 8-week follow up visit. Testing during this session will be considered as baseline testing for phase 2 intervention.

Visit 22-36: These sessions will involve the treatment sessions for the second intervention period. The opposite tDCS condition will be implemented here. For example, if a participant is randomly assigned to received “tDCS then sham”, the second intervention period will be 15 sessions of sham + language treatment.

Visit 37: 1-week follow up language testing after second intervention period.

Visit 38: 8-week follow up language testing after second intervention period.

Procedures for Screening (Visit 1)

The following procedures will be performed:

1. Administer the tDCS safety screening and MRI safety screening

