
Figure 1. Study Design

c. Blinding, including justification for blinding or not blinding the trial, if applicable.

Randomization and Blinding

The study is to be conducted in a double-blind manner. The subjects and the clinician, and the clinical staff involved in this study will not know the treatment assignment. Participant codes are programmed into the tDCS device so that the clinician administering the treatment only needs to enter the code to start stimulation without knowing whether those specific numbers are associated with tDCS or Sham. The PI will have access to the unblinded list of randomization codes and treatment assignments.

d. Justification of why participants will not receive routine care or will have current therapy stopped.

Participation in this study will not disrupt any current care or therapy.

e. Justification for inclusion of a placebo or non-treatment group.

All participants will be participants who will undergo active and sham conditions, thus serving as their own control.

f. Definition of treatment failure or participant removal criteria.

Date: 01/11/2019
Principal Investigator: [name]
Application Number: IRB00174879

Participants will be removed from the study if they are unable to comply with task instructions or tolerate the tDCS procedure.

g. Description of what happens to participants receiving therapy when study ends or if a participant's participation in the study ends prematurely.

When the study ends participants will continue to receive management with [name] or their own neurologist as usual (generally follow-up visits every about 6 months). If a patient's participation in the study ends prematurely s/he will still receive care as before. In sum, termination of the study or termination of participation in it will not affect regular therapy he or she may be receiving.

5. Inclusion/Exclusion Criteria

Participants in this study will have Primary Progressive Aphasia. Diagnostic evaluations will be conducted during the participants' initial visit to confirm aphasia diagnosis.

Inclusion Criterion:

- 1) Diagnosis of PPA, based on the PPA criteria (Gorno-Tempini et al., 2011) and presence of naming deficits
- 2) Capable of giving informed consent or indicating another to provide informed consent
- 3) 18 years of age or older.
- 4) Able to participate in language therapy tasks

Exclusion Criterion:

- 1) Did not speak English before the age of five
- 2) Less than 10 years of education

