For Aim 1, Hypothesis 1a This hypothesis states that Anodal tDCS (A-tDCS) plus VNeST therapy (A-tDCS+therapy) will significantly improve word retrieval of trained transitive verbs (from baseline to 1 week and 8 weeks post treatment). In the proposed study each participant will either receive tDCS (T) in the first intervention period followed by sham (S) in the second period (order = TS), or they will receive sham in the first period followed by tDCS (order = ST). For each participant, i , we will measure the change in word retrieval on the OANBtrained due to real tDCS stimulation by subtracting word retrieval performance accuracy on the OANBtrained before tDCS stimulation from the testing period 1 week following tDCS stimulation ($\delta Y_{i,tDCS}$). The identical measure will be computed for sham stimulation ($\delta Y_{i,sham}$). The data will be analyzed ($order_i, \delta Y_{i,tDCS}, \delta Y_{i,sham}$) for participants $i = 1, \dots, n$. Three models will be evaluated: the model of tDCS vs. sham, the model that adds the period effect, and the model that adds the interaction (a carryover effect). The predictive accuracy of these 3 models will be compared using the leave-one-out cross-validation R^2 . The model that best fits the data (the model with the highest R^2) will then be used to estimate the effect of tDCS relative to sham. This procedure will be repeated to determine changes from baseline to a period 8 weeks after treatment conclusion.

Sample Size Determination

We expect to enroll at least 50 participants with PPA over five years, and expect 45-50 will complete the study. This sample size is based on data collected from a separate study, IRB protocol number NA_00078932, PI [name]. *The effect size for anodal tDCS stimulation was 0.6 for trained items and 1.5 for untrained items.* We determined the number of participants to study, in order for the analysis to have 80% power to detect an effect size as low as 0.6. Allowing for 10% attrition, a sample size of 50 was chosen.

Missing Data

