We plan to minimize missing data by avoiding prolonged intervals between stimulations: 2 months may seem long with regard to the literature, but it is a reasonable length of time to be able to determine sustainability of any therapy. To minimize possible biases, analyses will be by intention to treat; any missing data will be addressed with the technique of multiple imputation (Rubin, 2004), generally recognized as best for handling missing data (Little et al., 2012).

Secondary Analyses

For Aim 1, Hypothesis 1b This hypothesis states that A-tDCS+therapy will generalize to other untreated verbs and nouns from baseline to 1 week and 8 weeks post treatment. The analyses will be identical to those described for Aim 1, Hypothesis 1a, except data from untreated verbs (OANBuntrained) and OANBnouns (untrained) will be used.

Aim 1, Hypothesis 1c Hypothesis 1c states that combined A-tDCS+therapy will result in greater improvement in functional communication skills compared to sham+therapy. Changes to functional communication skills resulting from A-tDCS+therapy vs. sham will be assessed using the ASHA FACS scale.

For Aim 2, Hypothesis 1: The proposed study aims to determine which patterns of baseline atrophy will predict the best response to A-tDCS plus a verb treatment using sentence building in individuals with PPA. People with more IFG damage tend to have more trouble with verbs, so we predict they are likely to show the most change in the primary outcome variable (OANBtrained verbs) with A-tDCS+therapy. It is possible that this hypothesis is incorrect, and they will show the least benefit from tDCS due to atrophy in IFG. It may be that people with more atrophy in other areas are going to benefit the most. Confirmation of either hypothesis will help select the best candidates for treatment. The area of peak atrophy (greatest difference between volume of each of the parcels on the JHU-MNI atlas in the participant compared to controls) will be identified for each participant. We will group participants by area of peak atrophy, and compare groups for each outcome variable, using Kruskal-Wallis one-way analysis of variance, for each outcome variable. As an exploratory analysis, we will also evaluate Spearman's correlations between the primary outcome variable and baseline volume in 5 regions of interest (areas affected in PPA: left IFG, left inferior temporal gyrus, left temporal pole, left superior temporal gyrus, and left supramarginal gyrus).

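### Section 4f ends study participation after randomisation with no later outcome testing, which undermines the promised intention-to-treat analysis and leaves possibly informative gaps to imputation

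*Combined protocol and SAP*

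**What the plan says.** Section 4f gives the removal rule: "Participants will be removed from the study if they are unable to comply with task instructions or tolerate the tDCS procedure". Removal is from the study, not from stimulation alone, and the rule is not tied to one condition or period.

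Section 4g covers what follows: "If a patient's participation in the study ends prematurely s/he will still receive care as before". It mentions clinical care but no further language testing.

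The Missing Data part of Section 7c says: "To minimize possible biases, analyses will be by intention to treat; any missing data will be addressed with the technique of multiple imputation". It gives no missingness assumption, no imputation model and no sensitivity analysis.

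The visit schedule in Section 4a fixes the timing of allocation: "Prior to the start of treatment, participants will be randomly assigned to receive either" one of the two orders. Failure on the screening task is dealt with earlier and separately, by discontinuing enrolment.

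The primary analysis in Section 7c needs a change score under each condition. The tDCS change is formed "by subtracting word retrieval performance accuracy on the OANBtrained before tDCS stimulation from the testing period 1 week following tDCS stimulation", and the sham change is formed in the same way.

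**The concern.** An intention-to-treat analysis needs outcomes on everyone randomised, including those who stop. Here the protocol itself ends outcome collection for a group defined by what happens after randomisation. Those people stay in the analysis only through imputed values.

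Their missing scores may differ from those of people who continued. In a progressive language disease, becoming unable to follow task instructions can reflect decline in the function that the Object and Action Naming Battery (OANB) measures. Intolerance could also differ between 20 minutes of real current and 30 seconds of sham, although the protocol does not expect this.

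At stake is what the trial estimates. With no data from anyone who stopped, the result drifts towards the effect in people able to complete the sessions. Data not collected cannot be recovered at analysis.

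**Working it through.** **1. What each removal loses.** From the visit list in Section 4a:

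| Removed during | Assessments lost | Change scores lost |
|---|---|---|
| Period 1 (Visits 5-19) | 20, 21, 37, 38 | Both conditions |
| Period 2 (Visits 22-36) | 37, 38 | Period 2 only |

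Visit 21 is both the 8-week follow-up of period 1 and the baseline of period 2. A period 1 removal therefore leaves only the initial baseline. A period 2 removal keeps a complete period 1 change score.

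**2. What imputation can draw on.** Under 4f and 4g nobody has an outcome measured after removal. Unless a further assumption is stated, the imputation model can learn only from participants who continued.

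**3. The plan's own figures.** Section 7c gives effect size 0.6 for trained items, 80% power, 10% attrition and N = 50. The attrition step is exact: 45 / 0.9 = 50. Alpha, sidedness and the SD behind 0.6 are not stated. I assume alpha 0.05 two-sided and first take 0.6 as standardised on the SD of a single change score, with zero within-person correlation:

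- Normal approximation: 2 × (1.96 + 0.84)² / 0.6² gives 44 after rounding up, and 44 / 0.9 gives 49.
- Paired t: 46, and 46 / 0.9 gives 52.

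Both are within 2 of 50, so the stated size reproduces on this reading. If 0.6 is instead standardised on the SD of the within-person difference, paired t needs 24, or 27 with attrition, which does not match 50.

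**4. Power is not the issue.** Two-sided paired t power:

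| Reading of 0.6 | 45 completers | All 50 |
|---|---|---|
| Zero correlation | 79.5% | 83.7% |
| SD of within-person difference | 97.6% | 98.6% |

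Expected attrition is already allowed for. What remains is bias.

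**5. Illustrative bias, first scenario.** Assume k of 50 stop in the active period, gain no tDCS benefit, and are imputed like continuers, whose effect is 0.6. The intention-to-treat effect is 0.6 × (1 − k/50), and the overstatement is 1/(1 − k/50) − 1.

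| k | Intention-to-treat effect | Overstatement |
|---|---|---|
| 2 | 0.576 | 4.2% |
| 3 | 0.564 | 6.4% |
| 5 | 0.540 | 11.1% |

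**6. Illustrative bias, second scenario.** Assume a fraction m is removed and their mean treatment difference is D SD below that of completers. The completer estimate is then too high by m × D.

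- m = 5%, D = 0.25 to 1.0: 0.0125 to 0.05 SD, or 2% to 8% of 0.6.
- m = 10%, D = 0.25 to 1.0: 0.025 to 0.10 SD, or 4% to 17% of 0.6.

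The documents give neither D nor a removal rate by condition. If D is zero there is no bias; if D is negative the sign reverses.

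**The case against.** The best defence is that 4f never takes anyone out of the analysis set. Intention to treat combined with imputation of any missing data can keep removed participants in as randomised. That stands. A reader might infer that 4f contradicts intention to treat outright, but the documents do not go that far. What they show is a rule that removes the data on which that analysis depends.

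A reader might also infer that removals are tied to active stimulation, so that the error favours tDCS. The documents do not support this. On sham, the Background says "In the sham condition, stimulation is applied for 30 seconds, and then rapidly ramped down", against 20 minutes for real stimulation, which makes a difference possible. It goes on: "The participant generally only feels the first 30 seconds of real or sham stimulation, and so cannot distinguish the two conditions". Section 8a cites mild itching that never caused a study to be stopped, Section 5 excludes people with scalp sensitivity, and the same rule applies under blinding in both periods. The compliance limb concerns a therapy task given in both conditions, and the 65% screening threshold filters part of it beforehand. If later non-compliance follows progression, it follows time, and order is randomised.

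Nor is 11% an estimate. It needs all the budgeted attrition to be active-period stopping with no benefit. The plan expects 45 to 50 completers, so removals could be zero.

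Finally, follow-up cannot repair everything. Visits 37 and 38 have no defined timing for someone who never starts period 2. A change score from a period with neither stimulation nor therapy would not measure that period's assigned condition. Some people who cannot follow task instructions may also be unable to complete the OANB. These limits are accepted and shape the fix.

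**Conclusion.** The point holds as an avoidable weakness that should be corrected. Sections 4f and 4g, read together, end outcome collection after randomisation for a group whose outcomes may differ, and the Missing Data section offers no means of learning about or testing that difference. This undermines the intention-to-treat analysis without formally contradicting it.

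The conclusion does not require removals to differ between conditions; it rests on removal ending assessment, which is the natural reading of 4f with 4g. The 4% to 11% range depends entirely on the first scenario's assumptions and serves only for scale. If few participants are removed, the practical effect will be small.

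**What to change.** Reconcile 4f and 4g with the Missing Data section:

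1. State that meeting 4f does not end outcome follow-up.
2. Still offer the 1-week and 8-week assessments for the period in which the participant stopped (Visits 20 and 21, or 37 and 38), timed from the planned end of that period, and analyse them under the randomised order.
3. Limit multiple imputation to assessments not obtained and to periods never started.
4. Record the reason, period and timing of stopping, use them in the imputation model, and state the missingness assumption.
5. Add a sensitivity analysis in which those who stopped are not assumed to respond like those who continued.

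The cost is a few lines of text and a few test visits, for perhaps 0 to 5 participants if the attrition allowance is a guide. These visits are already in the schedule, and Section 4a allows testing at home. The downside is extra testing for people who have stopped, some of whom may decline or be unable to do it. When stimulation or therapy should stop is a clinical matter on which no view is taken.

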- 3) Not medically stable
- 4) Picture naming ability below 10%
- 5) Picture naming ability above 85%
- 5) Significant history of drug or alcohol abuse or psychiatric or neurologic problems affecting the brain (other than PPA)
- 6) Non-MRI compatible pacemaker, implanted ferrous metal, claustrophobia, or other MRI contraindication
- 7) Seizures during the previous 12 months
- 8) Uncorrected visual loss or hearing loss by self-report
- 9) Use of medications that substantially lower the seizure threshold (e.g., methylphenidate) or use of NMDA antagonists (e.g., memantine)
- 10) History of brain surgery or any metal in the head
- 11) Scalp sensitivity (per participant report).

6. Drugs/ Substances/ Devices

a. The rationale for choosing the drug and dose or for choosing the device to be used.

tDCS has been established as a valid and reliable tool for at least temporarily affecting brain and behavior with minimal risks. Stimulation will be delivered by a battery-driven constant current stimulator (Soterix device, or a comparable model). The stimulator is not connected to a mainline power source and cannot produce in excess of 4mA of current. We will use non-metallic, conductive rubber electrodes covered by

Date: 01/11/2019
Principal Investigator: [name]
Application Number: IRB00174879

saline-soaked sponges to minimize the potential for chemical reactions at the interface of the scalp or skin and the electrodes.

b. *Justification and safety information if FDA approved drugs will be administered for non-FDA approved indications or if doses or routes of administration or participant populations are changed.*
N/A

c. *Justification and safety information if non-FDA approved drugs without an IND will be administered.* N/A

7. Study Statistics

a. Primary outcome variable

The primary outcome variable will be trained verbs on the OANB (OANBtrained) (pre-treatment and 1-week post-testing). To assess change in naming ability, the primary outcome in this study, the OANB) will be administered.

b. Secondary outcome variables

We will evaluate the effect of tDCS versus sham on change in naming of untrained verbs and nouns, and determine which pattern of atrophy is associated with the best treatment outcome.

c. Statistical plan including sample size justification and interim data analysis

Statistical Analyses

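### The primary tDCS effect comes from whichever of three models has the highest leave-one-out R², and the plan does not state which contrast is reported if the carryover model wins

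*Combined protocol and SAP*

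**What the plan says.** Section 7a makes trained verbs the primary outcome, at "pre-treatment and 1-week post-testing". Section 7c (Statistical Analyses, Hypothesis 1a) sets up one record per participant: order, change under tDCS and change under sham. It then lists tDCS versus sham, "the model that adds the period effect, and the model that adds the interaction (a carryover effect"). The choice among them is empirical: "The predictive accuracy of these 3 models will be compared using the leave-one-out cross-validation R^2", and the winner supplies the result ("the model with the highest R^2) will then be used to estimate the effect of tDCS relative to sham").

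The rule is used again at the later visit ("This procedure will be repeated to determine changes from baseline to a period 8 weeks after treatment conclusion") and for untrained verbs and nouns ("The analyses will be identical to those described for Aim 1, Hypothesis 1a"). Under Missing Data, "any missing data will be addressed with the technique of multiple imputation".

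The statistical plan gives no default model, no coding or contrast for the tDCS effect in the third model, and no test or significance level. No other section supplies them. Sections 2 and 4e justify the crossover on the ground that participants act as their own controls.

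**The concern.** In a two-period, two-order crossover, the first two models estimate the within-person tDCS-minus-sham difference. The third need not. Under the usual parameterisation of a carryover model, its treatment coefficient compares different people in period 1 only. A rule driven by predictive fit can therefore move the primary estimate from a within-person to a between-person contrast, and the plan does not say whether that is intended. At stake are the meaning of the primary estimate, some precision, some control of false positives, and whether results that sit side by side (1 week and 8 weeks, trained and untrained items, one imputed data set and the next) estimate the same thing.

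**Working it through.** **Inputs from the plan (section 7c).** 50 enrolled, 10% attrition, so 50 × 0.9 = 45 completers (taken as 23/22 by order); effect size 0.6; 80% power.

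**Assumptions, because the plan is silent.** Two-sided 5%; change scores with SD 1; within-person correlation ρ from 0 to 0.7; period effect 0 or -0.5 SD; leave-one-out by participant, which follows the one-record-per-participant layout.

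**1. The plan's own figure.** The sample size was chosen "in order for the analysis to have 80% power to detect an effect size as low as 0.6". With 0.6 scaled to the single-condition SD and ρ = 0, n = 2 × (1.96 + 0.84)² / 0.6² = 43.6, so 44; 44 / 0.9 = 48.9, so 49, close to 50. The choice of SD is not stated, so ρ = 0 is the reading that reproduces the plan.

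**2. What each model estimates.** Let τ be the tDCS effect, π the period effect, and λ any carryover into the period-2 change of those who had tDCS first.

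| Order | Period 1 mean | Period 2 mean | Mean of D = δY_tDCS − δY_sham |
|---|---|---|---|
| tDCS first | μ + τ | μ + π + λ | τ − π − λ |
| Sham first | μ | μ + π + τ | τ + π |

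- Treatment + period: the average of the two order means of D, τ − λ/2.
- Treatment only: the mean of D over all 45. With λ = 0 this is τ − π/45, which at π = -0.5 differs from τ by 0.5/45 = 0.011 SD. Without carryover the first two models are in practice the same quantity.
- Carryover model, period-1 contrast: τ, between people.
- Carryover model, averaged: (period-1 contrast τ + period-2 contrast τ − λ)/2 = τ − λ/2, identical to treatment + period.

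With participant as a fixed block, the interaction is aliased with order (48 columns, rank 47), so no separate third model exists.

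**3. Precision.** Treatment + period: SE = √[2(1 − ρ)/4 × (1/23 + 1/22)], which at ρ = 0 is √(0.5 × 0.0889) = 0.211. Period 1 only: SE = √0.0889 = 0.298. For 0.6 SD the ratios are 2.84 and 2.01, giving about 80% and 50% power. The variance ratio is 2/(1 − ρ): 2 at ρ = 0, 4 at 0.5, 6.7 at 0.7.

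**4. The selection rule, simulated without carryover.** The carryover model wins in about 8-17% of trials. False positives with zero period effect (40,000 trials each):

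| ρ | Selected, period-1 reading | Selected, averaged reading | Fixed treatment + period |
|---|---|---|---|
| 0 | 6.9% | 5.2% | 5.1% |
| 0.3 | 7.9% | 5.2% | 5.1% |
| 0.5 | 8.5% | 5.2% | 5.1% |
| 0.7 | 9.2% | 5.2% | 5.1% |

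Power for 0.6 SD at ρ = 0: 79.6% fixed, against 77.3% (no period effect) and 75.2% (period effect -0.5) for selection with the period-1 reading.

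When the carryover model wins at ρ = 0 with a true 0.6 SD effect, the two readings differ by a median of 0.43 or 0.37 SD (period effect 0 or -0.5) and disagree on significance in 47.2% or 46.5% of those trials. Over all trials that is 0.084 × 0.472 = 4.0% or 0.148 × 0.465 = 6.9%.

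**5. Repeats of the rule.** In a five-visit simulation with Visit 21 shared by both periods, exactly one of the 1-week and 8-week analyses picks the carryover model in about 9-22% of trials. With 5 of 50 missing period 2 and 20 imputations (assumed), some but not all imputed sets pick it in about 13-25%. Under the period-1 reading, those estimates target different contrasts and should not be pooled.

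**6. With true carryover.** At 0.5 SD the fixed model's bias is 0.5/2 = 0.25 SD, against 0.07-0.10 for the rule (period-1 reading). False positives are 21-38% fixed against 16-29% selected at ρ = 0 to 0.5, and 56-57% against 41-42% at 0.7. At 0.1-0.2 SD the fixed model has fewer false positives, and at 0.3 SD the two are about equal. At 0.5 SD the rule picks the carryover model in only 31-41% of trials. The period-1-only analysis stays near 5%.

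**The case against.** The rule is prespecified, and the third term is labelled carryover. In the standard model with treatment, period and carryover, the treatment coefficient is the period-1 contrast. A reader might infer that the effect is wholly undefined; the label does not support that. It points to one reading, although the plan never writes the contrast down, and that reading is the one that costs power and error control.

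The rule also gives some protection against carryover, and step 6 shows this is real when carryover is large. That stands: which single model to fix is partly a judgement about carryover. But a rule that misses carryover of 0.5 SD in most trials is a weak safeguard.

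A reader might also infer that carryover is likely because section 3 cites gains that lasted two months. That does not follow directly. Section 4a takes Visit 21 as the baseline for period 2 and the outcome is a change score, so a gain that simply persists subtracts out. Bias needs decay after Visit 21, a ceiling, or altered learning.

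**Conclusion.** The concern holds at should-fix level. The plan lets predictive fit decide whether the primary estimate is within-person or between-person, and does not state the contrast for the second case. Under the stated assumptions the consequence is modest: a few points of false-positive rate and of power, and none under the averaged reading. The gap in the text does not depend on those assumptions; every simulated figure does.

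Three stronger claims should not be made. First, that false positives exceed 10%: this arises only if the pairing is ignored and the within-person correlation is negative, against the one-record-per-participant layout. Second, that any disagreement between selected models across visits or imputations is harmful: swaps between the first two models leave the quantity essentially unchanged, and only switches to or from the carryover model matter. Third, that a fixed treatment + period model is better in every case: it is worse when carryover is near 0.5 SD.

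**What to change.** Replace the R² choice with one primary analysis at 1 week: treatment + period with within-participant inference. The estimate is the unweighted mean of the two order-specific means of δY_tDCS − δY_sham, with variance pooled within order, n − 2 degrees of freedom, a two-sided 5% test and a 95% confidence interval. Fit this model in every imputed data set and pool by Rubin's rules. Use it unchanged at 8 weeks and for untrained verbs and nouns. Report the treatment-only, carryover and period-1-only analyses as labelled sensitivity analyses, each with its contrast written out.

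The cost is plan wording and one degree of freedom, with no extra participants or data. The plan should acknowledge the exposure to carryover and point to the period-1-only analysis as the check, noting its power of about 50% for 0.6 SD. If the sponsor prefers another way to handle carryover, the contrast still has to be fixed before unblinding.
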